*** IF IN DOUBT, GIVE ADRENALINE ***

AFTER GIVING ADRENALINE:

[figure not shown]
- 1 Stay with child until ambulance arrives, **do NOT** stand child up
- 2 Commence CPR if there are no signs of life
- 3 Phone parent/emergency contact
- 4 If no improvement **after 5 minutes**, **give a further adrenaline dose** using a second autoinjectable device, if available.

You can dial 999 from any phone, even if there is no credit left on a mobile. Medical observation in hospital is recommended after anaphylaxis.

How to give EpiPen®

PULL OFF BLUE SAFETY CAP and grasp EpiPen. Remember: "blue to sky, orange to the thigh"

Hold leg still and PLACE ORANGE END against mid-outer thigh "with or without clothing"

PUSH DOWN HARD until a click is heard or felt and hold in place for **3 seconds**. Remove EpiPen.

Additional instructions:

This is a medical document that can only be completed by the child's healthcare professional. It must not be altered without their permission. This document provides medical authorisation for schools to administer a 'spare' back-up adrenaline autoinjector if needed, as permitted by the Human Medicines (Amendment) Regulations 2017. During travel, adrenaline auto-injector devices must be carried in hand-luggage or on the person, and **NOT** in the luggage hold. **This action plan and authorisation to travel with emergency medications has been prepared by:**

Sign & print name: _____

Hospital/Clinic: _____

Date: _____

Figure 4: Example of local national Allergy Management Plan

5.3.2.2 PREPARATION OF DOSES FOR PHASE 1 PRETREATMENT

The research team will prepare the doses for daily home administration during phase 1. On the initial escalation day visit, and at each subsequent updosing visit, the family will be provided with the required number of pre-labelled syringes, one for each day. Families will be asked to store the syringes in their home freezer at -18 to -22°C in a plastic container provided. Syringes will be taken out of the freezer 30 minutes prior to administration.

For children receiving ACTIVE treatment (groups S and O), the dose will contain the appropriate concentration of powdered milk (Protifar, Nutricia Ltd, Wiltshire, UK, containing 87.2 g cow's milk protein per 100g with equivalent casein/whey protein ratio as fresh milk). Children in group C will be given syringes containing a suspension of tapioca starch (Bob's Red Mill Natural Foods, Milwaukie, USA) as placebo, to maintain blinding (as needed). The same instructions will be followed for daily dose administrations for all participants.

Doses will be prepared in a designated food preparation area, following established food hygiene procedures. An unblinded member of the study research team (not be involved in the assessment of study outcomes) will prepare the doses in the first instance, according to a standard operating procedure. Each randomised participant will be allocated a labelled set of syringes, thus blinding of both the participant's families and local study team will be maintained.

5.3.3 HOME REACTIONS AND CONSEQUENTIAL CHANGES TO UPDOSING PROTOCOL

In the event of an allergic reaction to a dose of immunotherapy within 2 hours of a dose, either at updosing in hospital or after a dose given at home, the following measures will be taken:

- Families will be instructed to follow their Allergy Management Plan (example in Figure 4), and to contact the study team.
- Where a child is having objective symptoms consistent with possible anaphylaxis (e.g. wheeze, persistent cough, difficulty breathing, stridor or marked swallowing difficulties), families will be instructed to administer the adrenaline auto-injector pen provided and contact the study team on the Emergency number.

Once the study team has been informed, and following complete resolution of symptoms, the following plan of action will be recommended:

- For a single reaction consisting of wheeze, persistent cough, difficulty breathing, stridor or marked swallowing difficulties, the family must not give further doses without contacting the research team. The previous lower dose will be given the next possible day, preferably under medical observation on the Research Unit.
- For mild skin symptoms, itchy mouth, rhinoconjunctivitis or mild abdominal symptoms, reassurance to families will be provided and the current dose will be continued, with daily contact with the study team as needed.
- For persistent reactions for 3+days (within 2 hours of the immunotherapy dose) consisting of abdominal pain, rhinoconjunctivitis or skin symptoms, the local investigator should consider a dose reduction of 50% to be made until symptoms have mostly resolved.
- In the event of other symptoms that prove difficult to the child, the dose can be reduced at investigator's discretion.
- For recurrent symptoms, the local investigator may elect to offer participants an oral antihistamine during Phase 1, prior to dosing, to reduce allergic symptoms to immunotherapy doses, according to accepted clinical practice.

Where a dose reduction is required, the subsequent dose increase should be performed at least 2 weeks later at the Research Unit in hospital under supervision.

In the event of omitted doses:

- If 1-2 days of immunotherapy is missed, the subject can continue with the usual dose.
- If 3-4 days of immunotherapy are missed, the previous dose will be given until the subject can attend the research unit for repeat updosing.
- If more than 4 days are missed, dosing should stop until the subject can attend the research unit for repeat updosing.

Families will be requested to contact the research team in the event of an intercurrent illness, to discuss reducing the dose depending on symptoms and intensity.

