5.5.2 UPDOSING (PHASE 2)

Updosing in Phase 2 will be performed in a similar manner to that in Phase 1 (section **5.3.2.1**). At each updosing visit, the dose will first be given under medical supervision, followed by observation for at least one hour (2 hours if participant has previously experienced a delayed reaction). Participants will then take that dose daily at home for a minimum of 10 days, until the next updosing visit. Once the target dose is reached (step 16), participants will continue this dose on a daily basis until the final assessment at 1 year has been completed.

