5.9.1 EARLY STUDY TERMINATION

An Independent Data Monitoring Committee (IDMC) will assess study safety on a regular basis. The IDMC has the authority to suspend the study, or request withdrawal of a particular participant at any stage if it concludes there are significant safety concerns affecting a single participant or the study as a whole.

Recruitment to the study and further CM challenges and updosing will be suspended pending review by the IDMC in the event of:

- any death
- a participant being admitted to the intensive care unit for a study-related adverse event
- a participant experiencing a life-threatening anaphylactic reaction to an immunotherapy dose.

The IDMC will consider the circumstances and make a recommendation as to whether to terminate the study or continue with or without a protocol amendment.

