6.3 GRADING AND ATTRIBUTION OF ADVERSE EVENTS

Adverse events will be graded by the study site according to the criteria set forth in the NCI-CTCAE Version 3.0.²⁶ This document provides a common language to describe levels of severity to analyse and interpret data and to articulate the clinical significance of all adverse events:

- Grade 1 = mild adverse event.
- Grade 2 = moderate adverse event.
- Grade 3 = severe and undesirable adverse event.
- Grade 4 = life-threatening or disabling adverse event.
- Grade 5 = death.

All adverse events will be recorded and graded whether they are or are not related to disease progression or treatment. The NCI-CTCAE grades will be the primary source for scoring.

²⁶http://ctep.cancer.gov/protocolDevelopment/electronic_applications/docs/ctcaev3.pdf

Allergic reactions will be graded according to the CoFAR Grading System for Allergic Reactions, with additional modification to Grade 1 symptoms as shown in table 9. These can be used to inform as to the appropriate NTI-CTCAE grade.

Grade 1 – Transient	Grade 1- Mild	Grade 2 – Moderate	Grade 3 – Severe	Grade 4 – Life Threatening	Grade 5 - Death
Mild symptoms, <20mins. No impact on activity, no intervention needed. therapy required.	No or mild discomfort (< 48 hours).	Symptoms produce mild to moderate limitation in activity. Some assistance may be needed; no or minimal intervention/ therapy is required.	Marked limitation in activity. Some assistance usually required; hospitalisation is possible.	Extreme limitation in activity. Significant medical intervention is required; hospitalisation is probable.	Death
These symptoms may include pruritus, periorbital or facial angioedema, swelling or rash, mild abdominal discomfort, or other transient symptoms.		Hospitalization is possible but unlikely. These symptoms may include persistent hives, wheezing without dyspnea, abdominal discomfort / increased vomiting, or other symptoms	Symptoms may include bronchospasm with dyspnoea, severe abdominal pain, throat tightness with hoarseness, transient hypotension among others. Parenteral medication(s) are usually indicated.	Symptoms may include persistent hypotension and/or hypoxia with resultant decreased level of consciousness associated with collapse and/ or incontinence or other life-threatening symptoms.	

Table 9: CoFAR Specific Grading System for Allergic Reactions

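### After a life-threatening reaction to a dose, no rule holds the affected child's daily dose until the IDMC review, apart from a hold until the team is contacted and withdrawal after ICU admission during updosing or on the team's judgement

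*Combined protocol and SAP*

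**What the plan says.** Two parts of the protocol deal with what follows a severe reaction.

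Section 5.9.1 acts on the study. It says "Recruitment to the study and further CM challenges and updosing will be suspended pending review by the IDMC" after any of three events: a death, an intensive care admission for a study-related event, or "a participant experiencing a life-threatening anaphylactic reaction to an immunotherapy dose". The third is a trigger in its own right, so the protocol foresees a life-threatening reaction that does not lead to intensive care.

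Section 5.3.3 acts on the child's dosing. Its plan is a recommendation that applies once the team knows of the reaction and symptoms have fully resolved. The strictest bullet reads "For a single reaction consisting of wheeze, persistent cough, difficulty breathing, stridor or marked swallowing difficulties, the family must not give further doses" unless the research team has been contacted. It then continues: "The previous lower dose will be given the next possible day, preferably under medical observation on the Research Unit". Reactions outside the named categories come under a general bullet: "In the event of other symptoms that prove difficult to the child, the dose can be reduced at investigator's discretion". Section 5.5.4 carries the same measures into Phase 2, but cites 5.3.2.4, a section that does not exist; 5.3.3 is evidently meant.

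**The concern.** The 5.9.1 suspension is triggered by one child's reaction, yet the activities it lists do not include that child's daily dose. The 5.3.3 bullet is triggered by signs and has no severity ceiling, and its default is an early restart with hospital observation preferred but not required.

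Read together, the two sections allow an inverted result. Other children's updosing stops, while the child whose reaction caused the stop may be given milk again, possibly at home, before anyone independent has looked at the event. Avoiding that depends on a clinician choosing to depart from the recommended plan or using discretion. What is at stake is the safety of individual children.

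**Working it through.** The plan states no figure on this point. The check is a comparison of the rules, plus one piece of arithmetic on the dose tables.

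**1. What each rule does to the affected child's daily dose**

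| Rule | Effect on the daily dose | Holds until IDMC review? |
|---|---|---|
| 5.3.3, listed signs: contact the team | No further doses | No; ends once the team is contacted |
| 5.3.3, complete resolution | Plan starts only when symptoms have gone | No; ends with resolution |
| 5.3.3, listed signs: restart | One step lower, at the earliest opportunity | No |
| 5.3.3, other symptoms | Reduction at discretion | No |
| 4.3 with exclusion criterion 1 in 4.2 | Withdrawal after intensive care admission for an allergic reaction, if it arises in the updosing phase | Stops dosing, in that case only |
| 4.3, team's opinion | Withdrawal if continuing would harm the child | Stops dosing, if so judged |
| 5.9.1, suspension | Daily dose not named | No |
| 6.1 and 6.2 | Review by trial management; report to the IDMC | No dose action stated |

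The uncovered case is a life-threatening reaction without intensive care admission, between contact with the team and the IDMC review. Section 5.9.1 sets no deadline for that review.

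**2. Is a lower-dose restart already covered by the pause on updosing?** The wording suggests not. Section 5.5.2 describes a supervised increase at the visit and then says "Participants will then take that dose daily at home for a minimum of 10 days, until the next updosing visit", so the daily home dose and the updosing visit are different things. Section 5.3.3 likewise separates a dose reduction from the later supervised increase. When the authors want dosing itself to stop, they say so, as in the missed-dose rule: "If more than 4 days are missed, dosing should stop until the subject can attend the research unit for repeat updosing".

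**3. Which grades does the bullet reach?** Table 9 places "wheezing without dyspnea" in Grade 2 and bronchospasm with dyspnoea in Grade 3. A Grade 4 reaction with hypoxia can include difficulty breathing. All three involve a sign on the 5.3.3 list, and the list makes no distinction by grade. A Grade 4 reaction showing only hypotension or collapse has no listed sign and falls to the discretionary bullet.

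**4. How large is the restart dose?** Ratio = dose at step k − 1 ÷ dose at step k, from step 2 upwards.

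- Phase 1 (Table 4, 11 step changes): lowest 6 ÷ 15 = 40.0%; highest 30 ÷ 60 = 50.0%.
- Phase 2 (Table 6, 15 step changes): lowest 0.4 ÷ 1 = 40.0%; highest 135 ÷ 255 = 52.9%. At the top step, 2040 ÷ 4080 = 50.0%.

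The written restart is therefore roughly half the dose that caused the reaction.

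**The case against.** The strongest reply is that the protocol is better protected than 5.9.1 alone suggests. The bar on doses before team contact is mandatory. Withdrawal after intensive care admission during updosing does not depend on opinion. The team must withdraw a child whom continuation would harm, all anaphylaxis to doses is reviewed, and 8.2 leaves clinicians free to depart from the protocol. All of this stands, and it rules out a reading that a reader might be tempted by, that nothing written stops the child's dose.

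A second tempting reading is that the protocol orders a next-day dose after every Grade 4 reaction. The documents do not support it. The bullet describes a reaction made up of respiratory or swallowing signs, whereas Table 9 describes Grade 4 mainly by hypotension, hypoxia and collapse. For a purely cardiovascular reaction there is no written restart, only discretion. Where the bullet does apply, it is a recommendation that waits for full resolution.

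The missed-dose rule can also close the gap in part. A child off doses for more than 4 days may resume only by repeat updosing, which 5.9.1 has suspended. But that hold begins only after the fifth missed day, and the early restart works against reaching it.

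Two ways of sizing the problem should be resisted. A reader might compare the 2040 mg restart after a step 16 reaction with the 1.44 g entry limit. That limit was applied before desensitisation and appears to be cumulative (doses 1 to 7 in Table 2 sum to 1443.5 mg), and a child at step 16 would normally have taken 2040 mg daily for at least 10 days. A reader might also count the doses taken before the review, but the documents give no review time.

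**Conclusion.** The concern holds in this limited form. Three brakes exist: a hold until the team is contacted, withdrawal after intensive care admission during updosing, and withdrawal on the team's judgement. Beyond them, no rule holds the affected child's daily dose until the IDMC has reviewed a life-threatening reaction. With the listed signs, the recommended course is an early restart at 40 to 53% of the reacting dose, with observation only preferred. With other signs, the response is discretionary.

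The conclusion rests on two readings of the text: that a lower-dose restart is not updosing, and that the listed-signs bullet can apply to a life-threatening reaction that includes one of those signs. If the second is rejected, the dose response is discretionary and there is still no hold until review.

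The documents give no rate of life-threatening reactions, so the number of children cannot be stated and is probably small. This is a patient-safety point; nothing is claimed about the primary outcome. Because the harm could be grave and the change is nearly free, it should be made.

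**What to change.** **Section 5.9.1.** Add *and daily dosing of the affected participant* to the activities suspended pending IDMC review. State that any restart is at a dose set by the investigator after that review, with the first dose supervised on the Research Unit.

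**Section 5.3.3.** Add a line for reactions that are not life-threatening but are Table 9 Grade 3, or show cardiovascular or neurological signs. Home dosing is held until team review, then restarted no higher than the previous lower dose, with the first dose supervised on the Research Unit as a requirement. Leave the Grade 1 and 2 rules as written, including those for Grade 2 wheeze without dyspnoea, so that the two sets of rules do not overlap.

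**Editorial.** In 5.5.4, change the reference from 5.3.2.4 to 5.3.3.

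**Cost.** A clause and a sentence in 5.9.1, one line in 5.3.3 and one corrected reference. In practice, an occasional unscheduled supervised dose and a treatment pause for the affected child. If the pause exceeds 4 days, the existing missed-dose rule already requires attendance at the unit. No new data are collected and no endpoint changes.

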5.4 INTERIM POST-PHASE 1 ASSESSMENT (AROUND 6 MONTHS)

Subjects will be invited to undergo a DBPCFC to CM following completion of Phase 1 to again determine their threshold of reactivity to CM, according to Table 2 (Section 5.2.2). The pre-challenge assessment and challenge protocol are described in Section 5.2. Both challenge visits should take place with 28 days of each other. Subjects will also undergo repeat skin prick testing and HRQL assessments as described in section 5.8. Participants will continue their Phase 1 daily dosing until phase 2 is commenced.

5.5 PHASE 2 - CONVENTIONAL ORAL IMMUNOTHERAPY

In phase 2, subjects will receive daily oral CM doses at home in an open, unblinded manner. Dose increases will be performed under medical supervision on the research Unit following the regime depicted in Table 6 ("conventional OIT"). Phase 2 will last 6 months (26 weeks) from the first updosing visit of Phase 2.

The protein content of supermarket-sourced commercial milk is 3.4g/100ml in UK and 3.0g/100ml in Spain. Therefore, the volume of milk to be delivered will vary slightly, by study site, in order to achieve the same dose of CM Protein across study sites (Table 6).

PHASE 2 UPDOSING PROTOCOL (CONVENTIONAL OIT)						
Step	Target CM protein (mg)	Supermarket milk (ml)	Milk preparation	Final dose (ml)		
	UK	SPAIN		UK	SPAIN	
1	0.04	0.0012	0.0013	0.125	0.15	
2	0.08	0.0024	0.0027	0.25	0.3	
3	0.2	0.0059	0.0067	0.6	0.7	
4	0.4	0.0118	0.0133	0.12	0.15	
5	1	0.0294	0.0333	0.3	0.35	
6	2.5	0.0735	0.0833	0.75	0.8	
7	6	0.175	0.2	0.2	0.2	
8	15	0.45	0.5	0.4	0.5	
9	30	0.9	1.0	0.9	1.0	
10	60	1.75	2.0	1.75	2.0	
11	135	4.0	4.5	4.0	4.5	
12	255	7.5	8.5	7.5	8.5	
13	510	15	17	15	17	
14	1020	30	34	30	34	
15	2040	60	68	60	68	
16	4080	120	136	120	136	

Table 6. Phase 2 updosing protocol (conventional OIT)

Although there are 16 steps to the OIT protocol in Phase 2, we expect at least 95% of participants to be able to commence the protocol at Step 7+ (i.e. with undiluted supermarket-sourced milk), and thus complete the full protocol within the 6 months allocated:

- Over two thirds of participants (i.e. those in groups S and O) are expected to reach 60mg CM protein by the end of phase 1, which corresponds to step 10.
- On the basis of population threshold data for cow's milk, we expect 90% of participants (even those receiving placebo in phase 1) to tolerate step 7 (6mg CM protein).

The inclusion of Steps 1-6 are to allow those few participants who remain very sensitive to low doses of CM protein to continue to participate in the study.

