5.5.1 INITIAL UPDOSING / DOSE ESCALATION DAY

The starting dose of OIT in phase 2 will be individualised based on the outcome of the interim DBPCFC at 4-7 months, as shown in Table 7. The NOAEL (No Observed Adverse Event Level or highest dose not triggering symptoms) will be used as the tolerated dose. Mild transient symptoms (e.g. itchy mouth) to the reference dose (transient COFAR Grade 1 symptoms (Table 9) might be acceptable.

Tolerated dose (NOAEL) at 6 months DBPCFC	Initial dose for Phase 2 OIT		Max dose at Initial Escalation day	
	Step	CM Protein (mg)	Step	CM Protein (mg)
<0.5mg (i.e. 1 st dose reactor at FC)	1	0.04	6	2.5
0.5mg	3	0.2	6	2.5
3mg	4	0.4	7	6
10mg	6	2.5	8	15
30mg	9	30	n/a	n/a
100mg	10	60	n/a	n/a
300mg	10	60	n/a	n/a
1000mg or more	11	135	n/a	n/a

Table 7. Starting dose for OIT in Phase 2.

Participants starting phase 2 OIT at steps 1-6 will be offered to attend an escalation day visit at which up to 6 consecutive doses will be given by mouth at 20-30 minutes intervals under medical supervision on the Research Unit. As described in 5.3.2.1 (phase 1 escalation day), the supervising clinician will assess the participant to ensure suitability prior to dosing. If a given dose triggers symptoms that cause discomfort to the participant or deemed significant by the research team, no further doses will be administered on that day. Participants will be observed for at least one hour after dosing (2 hours if participant has previously experienced a delayed reaction). Participants will be instructed to have the last well-tolerated dose at home on a daily basis for a minimum of 10 days, until the next increase is performed.

At the discretion of the local investigator, participants commencing phase 2 OIT at step 9 or above do not need to attend for a separate escalation day:

- If the 2nd DBPCFC visit (at 6 months) is ACTIVE, then they can start the OIT dose the next day at home, unless there is doubt as to the dose tolerated at challenge (in which case a separate initiation visit should take place).
- If the 2nd DBPCFC visit is PLACEBO, then the initial OIT dose(s) can be given at the end of the 2 hour observation period of the challenge, where time permits.

Participants will then be asked to have their daily dose at home for a minimum of 10 days until the next increase is performed.

Prior to discharge home, patients will receive instructions including symptoms management and reporting as described in **5.3.2.1**.

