5.5.3 DOSE PREPARATION FOR PHASE 2 OIT

Locally-sourced supermarket milk will be used for doses. Parents will receive written instructions on how to give doses at home.

The majority of participants are expected to start home dosing beyond step 9 i.e. with undiluted pasteurised milk available at supermarkets. For those few participants where diluted doses (steps 1 to 6) are needed, these will be provided with pre-labelled individual syringes containing the daily dose for the appropriate step. Families will be asked to store the syringes in their home freezer at -18°C in a plastic container. Each syringe will be used for a single dose, with the syringe taken out of the freezer 30 minutes prior to administration.

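### Table 6 gives two different UK volumes for the same undiluted dose at Phase 2 steps 7 and 8; the final-dose cells deliver 6.8 and 13.6 mg against labels of 6 and 15 mg

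*Combined protocol and SAP*

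**What the plan says.** All of this is in the combined protocol and SAP.

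- Section 5.5 gives the concentrations: "The protein content of supermarket-sourced commercial milk is 3.4g/100ml in UK and 3.0g/100ml in Spain". It adjusts the volumes by country "in order to achieve the same dose of CM Protein across study sites (Table 6".
- Section 5.5 describes a start at step 7 or later as "i.e. with undiluted supermarket-sourced milk". Section 5.5.3 agrees, tying dilution to the earlier rows: "For those few participants where diluted doses (steps 1 to 6) are needed".
- Table 6, step 7 (target 6 mg): milk volume UK 0.175 ml, Spain 0.2 ml; final dose UK 0.2 ml, Spain 0.2 ml.
- Table 6, step 8 (target 15 mg): milk volume UK 0.45 ml, Spain 0.5 ml; final dose UK 0.4 ml, Spain 0.5 ml.
- Table 7 (section 5.5.1) uses the same labels. A child whose NOAEL at the interim challenge is 3 mg may go up to step 7, labelled 6 mg, on the escalation day. A child with NOAEL 10 mg may go up to step 8, labelled 15 mg.
- What is tolerated that day is then taken home: "Participants will be instructed to have the last well-tolerated dose at home on a daily basis for a minimum of 10 days". For home dosing, section 5.5.3 says "Parents will receive written instructions on how to give doses at home".

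No rounding rule is given for Table 6.

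**The concern.** An undiluted dose has one volume. At UK steps 7 and 8 the table prints two, and they lead to different amounts of allergen. Site staff cannot tell from the table which one governs, and the column headed as the final dose is the natural one to follow. If they follow it, the UK and Spanish centres give different amounts of protein at a step carrying the same label, which is what the country-specific volumes were meant to prevent. The numbers are operative: they set what milk-allergic children swallow, first in the unit and then daily at home.

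**Working it through.** **Inputs.** UK milk: 3.4 g/100 ml = 34 mg/ml. Spanish milk: 3.0 g/100 ml = 30 mg/ml (section 5.5). Targets and volumes are from Table 6. Steps 7 to 16 are undiluted (sections 5.5 and 5.5.3).

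**Formulas.** Volume needed = target mg / concentration. Delivered mg = volume × concentration.

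**Rows that reproduce.** In Spain the two volume columns agree at steps 7 to 16 and hit the target exactly; for example, step 7 is 0.2 × 30 = 6.0 mg and step 8 is 0.5 × 30 = 15.0 mg. In the UK the two columns agree at steps 9 to 16:

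- step 9: 0.9 × 34 = 30.6 mg (+2.0%)
- step 10: 1.75 × 34 = 59.5 mg (-0.8%)
- step 11: 4.0 × 34 = 136 mg (+0.7%)
- steps 12 to 16: exact

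**The two rows that do not reproduce (UK).**

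| Step | Target | Exact volume | Milk column | Final-dose column |
|---|---|---|---|---|
| 7 | 6 mg | 6/34 = 0.176 ml | 0.175 × 34 = 5.95 mg (-0.8%) | 0.2 × 34 = 6.8 mg (+13.3%) |
| 8 | 15 mg | 15/34 = 0.441 ml | 0.45 × 34 = 15.3 mg (+2.0%) | 0.4 × 34 = 13.6 mg (-9.3%) |

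In mg, the final-dose cells miss the label by 6.8 - 6 = +0.8 and 13.6 - 15 = -1.4. The final-dose cell differs from its own milk cell by 0.2/0.175 = +14.3% at step 7 and 0.4/0.45 = -11.1% at step 8.

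**Size of the steps (UK).**

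| Increase | Target | Final-dose column as printed | Using the milk column |
|---|---|---|---|
| 7 to 8 | 15/6 = 2.5 | 13.6/6.8 = 2.0 | 15.3/5.95 = 2.57 |
| 8 to 9 | 30/15 = 2.0 | 30.6/13.6 = 2.25 | 30.6/15.3 = 2.0 |

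**Who meets these rows.** By Table 7, children with an interim NOAEL of 30 mg or more start at step 9 or above. Steps 7 and 8 are therefore reached by UK children with NOAEL of 10 mg or less, and by any child who has to step back after a reaction. A child with NOAEL 10 mg has already tolerated a 10 mg challenge dose, more than 6.8 mg. So the step 7 excess lies above the challenge-tolerated dose only where NOAEL is 3 mg or less, and there the 6 mg target already does so.

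**The case against.** The best defence is that this is a missing footnote. The exact UK volumes, 0.176 and 0.441 ml, round to 0.2 and 0.4 ml at one decimal. The mg column is headed as a target, and the protocol allows volumes to vary slightly between sites. Steps 1 to 6 come as pre-filled syringes, whereas from step 7 families probably measure the milk themselves, so coarser volumes would be sensible. This is plausible and may be the true explanation. But it is an inference: no rule is stated, step 10 keeps 1.75 ml, and Tables 6 and 7 still label the doses 6 and 15 mg beside a conflicting milk volume.

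A second defence is that the table reached us through text extraction and its preparation column is blank. That does not explain the mismatch. The text establishes that steps 7 and 8 are undiluted, and the agreement at UK steps 9 to 16 and Spanish steps 7 to 16 shows that the columns are aligned. The blank column does mean that no conclusion should be drawn about delivered doses in the diluted rows.

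A third point stands in full: the safeguards limit the harm. Escalation and updosing doses are first given under supervision (sections 5.5.1 and 5.5.2), and if significant symptoms occur on the escalation day, "no further doses will be administered on that day".

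A reader might infer more in three directions, none of which the documents support.

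- *A general overdose of sensitive UK children.* Step 8 is an under-dose, and the step 7 excess matters relative to challenge tolerance only at NOAEL of 3 mg or less.
- *A head count.* The plan says "we expect 90% of participants (even those receiving placebo in phase 1) to tolerate step 7 (6mg CM protein", but that expectation covers both centres and does not measure passage through steps 7 and 8. The UK number is unknown.
- *A bias in S versus C, or proof that there is none.* Both arms at a centre use the same volumes and allocation is stratified by centre (section 5.3.1). However, the starting step depends on the threshold after Phase 1, so if pretreatment raises thresholds, placebo children would meet these rows more often. With differences this small and in opposite directions, any effect is probably negligible, but stratification alone does not make it zero.

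**Conclusion.** The inconsistency is real and should be corrected; it belongs at the bottom of the minor category. At UK steps 7 and 8 the final-dose cells contradict the milk cells in the same rows and miss the labelled dose by +0.8 mg (+13.3%) and -1.4 mg (-9.3%). At these two steps the table does not meet its stated aim of equal protein at both sites. The conclusion rests on the protocol's milk concentrations and on steps 7 and 8 being undiluted. Whether the cause is deliberate rounding or a slip cannot be settled from the documents. Nor can we tell which volume families are actually given, because the UK written instructions are not included.

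**What to change.** Set the UK final doses in Table 6 to 0.175 ml at step 7 (5.95 mg) and 0.45 ml at step 8 (15.3 mg), and check that the UK dosing instructions say the same.

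If rounding to 0.1 ml is intended so that families can measure the dose, keep 0.2 and 0.4 ml. In that case state the rounding under Table 6 and show 6.8 and 13.6 mg as the delivered UK doses in Tables 6 and 7.

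The cost is two cells or one footnote, plus a check of the instructions. Changing the cells has a downside: the UK step 7 to 8 increase goes from 2.0-fold to 2.57-fold, slightly above the 2.5 target, and 0.175 ml needs a finely graduated syringe. The footnote avoids both but leaves the two centres giving different doses at these steps. Neither option changes the visits, sample size or analysis.
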